The glutamate N-methyl-D-aspartate (NMDA) receptor antagonist ketamine is an FDA approved general anesthetic with immediate calming effects (within 24 hours). Ketamine has proved to have great utility for emergency procedures and management of chronic pain syndromes. In psychiatry ketamine has been shown to induce a rapid antidepressant response in patients with Treatment Resistant Depression (TRD) following a 0.5 mg/kg dose administered intravenously over 40 minutes. These benefits were maintained for approximately 1 week post-infusion (Murrough et al., 2011). There is also a significant body of evidence for the mood-enhancing and anti-suicidal properties of ketamine in patients with bipolar and unipolar depression (Griffith et al. 2014). This promising area of research poses a variety of methodological challenges. The optimal dose of ketamine for therapeutic purposes is still unknown but previous studies have used doses of ketamine of up to 0.5 mg/kg (Kollmar et al., 2008; Messer et al., 2010; Murrough et al., 2011; Rasmussen et al., 2013; Stefanczyk-Sapieha et al., 2008; Zanicotti et al., 2012). Ketamine administration requires close anesthetic monitoring in most institutions. As a result, the administration of ketamine involves major costs that insurance companies and patients cannot afford (Rasmussen et al., 2013). Thus, much work is still needed to increase/maintain high response rates to ketamine and lower the costs associated with administration.

The *primary objective* of our study is to determine the effectiveness of serial infusions of intravenous (IV) ketamine in adults *with treatment resistant depression (TRD) - diagnosed with either Major Depressive Disorder or Bipolar Disorder* - at a slower infusion time than reported in previous studies. We expect that this approach alongside with the presence of a psychiatrist with Advanced Cardiac Life Support (ACLS) training will eliminate the need for continuing anesthetic monitoring during infusion, thus leading to a more cost-effective intervention. As part of this objective, we plan to recruit 30 individuals with Treatment Resistant Depression and conduct an open label, naturalistic study using slow infusions of ketamine over a time period of 40 minutes. **The duration of this study will be 12 weeks and will include twice weekly infusions over a period of 4 weeks and weekly infusions for the following 4 weeks of the study treatment period (8 weeks). There will also be a 4 week observational period post- treatment.**

Our *hypotheses* are that patients suffering from TRD receiving weekly slow IV infusions of ketamine (0.5 mg/kg) over 40 minutes will:

1. Report similar efficacy and better tolerability than those reported with conventional schemes of 3 infusions per week over a 12 day period.
2. Report less psychiatric side effects measured by changes in test scores on the Montgomery-Åsberg Depression Rating Scale (MADRS), Quick Inventory of Depressive Symptomatology (QIDS) and Young Mania Rating Scale (YMRS) compared to those previously reported with conventional schemes of serial ketamine infusions.
3. Report an almost immediate effect based on the PANSS and Q-LES-Q scales which will be administered after the 40 min infusion period.
4. Report less suicidal ideation measured by changes in scores on the Scale for Suicide Ideations (SSI; Beck et al., 1979), and the Suicide Status Form (SSF; Conrad et al., 2009) scores compared to that previously reported with conventional schemes of serial ketamine infusions.
5. Report a better global outcome of treatment measured by a decrease in scores on in the Clinical Global Impression Scale (CGI; Guy, 1976) score compared to that previously reported with conventional schemes of serial ketamine infusions.
6. Experience less hemodynamic changes in blood pressure and heart rate compared to than those previously reported with conventional schemes of serial ketamine infusions.
7. Experience no cognitive impairment on the Brief Assessment of Cognition in Affective Disorders (BAC-A) following ketamine infusions. To our knowledge this hypothesis has not been previously assessed after an 8-week serial ketamine infusion treatment period.

Clinical relevance

Treatment Resistant Depression (TRD) is a major public health problem that constitutes a great burden for patients and mental health providers because of its prevalence, impact on people's quality of life and overall cost to the society (Nemeroff et al., 2007). Given the dearth of the research in the field of Ketamine treatment, more naturalistic follow-up studies focusing on ketamine's innovative antidepressant properties are warranted. Further, the findings of this study will provide health professionals with additional knowledge on the antidepressant properties of repeated ketamine IV infusions in both resistant Major Depressive Disorder (MDD) and Bipolar Disorder (BD). The current study will also help characterize responders from non- responders to ketamine, and will enable the assessment of the response and remission rates following ketamine intervention.

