The results of the largest study conducted thus far on the antidepressant effects of repeated ketamine infusions included twenty-four subjects with TRD who underwent a washout of antidepressant medication followed by a series of up to six intravenous (IV) infusions of ketamine (0.5 mg/kg) over 40 minutes administered open-label three times weekly over a 12- day period (Murrough et al., 2013b). The TRD patients meeting response criteria were monitored for depressive relapse for up to 83 days from the last infusion. The antidepressant effect of ketamine was evident very early in the course of treatment. Moreover, ketamine exerted a broad-spectrum effect on individual symptoms of depression, and rapid response to the first infusion was highly predictive of a sustained response to subsequent infusions (Murrough et al., 2013b). Although preliminary, ketamine's large and sustained effect size regarding its antidepressant properties seems to be carried over repetitive IV infusions. In particular, suicidal ideation (SI) rapidly decreases even among non-responders to repetitive ketamine IV infusions. Therefore, ketamine is suggested to exert a unique anti-SI effect even in the absence of a full antidepressant response (Murrough et al., 2013b). This finding is consistent with previous reports highlighting the potential anti-SI effects of single dose infusion of IV ketamine in depressed populations (Diaz-Granados et al., 2010b; Larkin and Beautrais, et al 2011; Price et al., 2009).

Recently, researchers at the Mayo Clinic have performed serial ketamine infusion but at a lower infusion rate (Rasmussen et al., 2013). Ten depressed patients were treated with twice weekly

infusions of ketamine 0.3 mg/kg administered over 100 min until either remission was achieved or four infusions were given. Patients were naturalistically followed weekly for four weeks after completion of the infusions and psychiatric side effects were assessed with the Young Mania Rating Scale (YMRS; Young et al., 1978) and the Brief Psychiatric Rating Scale (BPRS; Overall and Gorman, 1988) respectively. While a 50% remission rate was documented without any significant increase on BPRS or YMRS measures, only two patients maintained remission at the 4-week follow up session. Nonetheless, it seems that ketamine infusions at a lower rate than previously reported might produce similar efficacy, excellent tolerability, and thus may be more available for routine clinical care.

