Ketamine infusions do not appear to have negative neurocognitive sequels. In a recent study, 15 patients with TRD underwent six IV infusions of 0.5 mg/Kg ketamine over 40 min, (three times a week during a 12-day period) followed by a 4-wk observational period. Following the last ketamine infusion the authors observed an improvement in visual memory and working memory. These cognitive changes may have been due to the decrease in the severity of the depressive symptoms (Shiroma et al. 2014). Along the same line, Murrough et al. (2015) found no change in cognitive functioning 7 days post-ketamine treatment in individuals with treatment-resistant depression.

To the best of our knowledge, the only published study exploring the tolerability, safety, and efficacy of repeated-dose open-label IV ketamine (six infusions over 12 days) focused on 10 medication-free symptomatic patients with TRD who had previously shown a meaningful antidepressant response to a single ketamine dose (Aan het Rot, et al., 2010). Patients received a 40-min IV infusion of ketamine (0.5 mg/kg) in an inpatient setting with continuous vital-sign monitoring and repeated recording of adverse events such as psychotomimetic effects. In the event that patients showed a 50% reduction in MADRS scores on day 2, they received five additional infusions on an outpatient basis on days 3, 5, 8, 10, and 12. Follow-up visits were conducted twice weekly for 4 weeks or until relapse. Ketamine elicited minimal transient positive psychotic or dissociative symptoms. Side effects during and after each ketamine infusion although common were reportedly mild. The response criterion was met by nine patients after the first infusion as well as after the sixth infusion of ketamine. MADRS scores after the sixth ketamine infusion were reduced by 85%, and an 89% relapse rate was reported between weeks 3 and 4 after finishing repeated IV ketamine infusion.

To summarize, these findings confirm the feasibility of low concentration and slower infusion rate of repeated-dose IV ketamine infusions for the acute treatment of TRD in the clinical practice (Aan het Rot, et al., 2010; Murrough et al., 2013b; Rasmussen et al., 2013).

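### The primary objective claims a slower infusion than earlier studies used, but 0.5 mg/kg over 40 minutes is the rate of the conventional series; only the schedule is new

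*Combined protocol and SAP*

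**What the plan says.** The primary objective, in the opening section of the combined protocol and SAP, is the effectiveness of serial IV ketamine "at a slower infusion time than reported in previous studies". The stem of the hypotheses then describes the treatment as "patients suffering from TRD receiving weekly slow IV infusions of ketamine (0.5 mg/kg) over 40 minutes". Section 2.0, B. Innovation, gives a new dose and infusion time as the first of two reasons why the approach is novel.

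The same document describes earlier work as follows:

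- The introduction reports a rapid antidepressant response in TRD "following a 0.5 mg/kg dose administered intravenously over 40 minutes".
- Section 2.0, A. Significance, describes a 24-patient study as a "series of up to six intravenous (IV) infusions of ketamine (0.5 mg/kg) over 40 minutes administered open-label three times weekly", given over 12 days.
- The same section describes a neurocognitive study in which "15 patients with TRD underwent six IV infusions of 0.5 mg/Kg ketamine over 40 min", and a medication-free series of 10 patients at the same dose and duration.
- It also describes a second 10-patient series, given "infusions of ketamine 0.3 mg/kg administered over 100 min".

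The primary objective adds an expectation that the approach, with an ACLS-trained psychiatrist present, "will eliminate the need for continuing anesthetic monitoring during infusion, thus leading to a more cost-effective intervention". Section C. Approach has an anesthesiologist start each infusion and stay until the patient is awake and stable.

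**The concern.** The objective names a property that the treatment does not appear to have. Slowness is also part of the reasoning for the expected benefits: better tolerability (hypothesis 1), smaller hemodynamic changes (hypothesis 6) and less need for anesthetic monitoring. If the rate is the same as in the conventional series, a favorable comparison with the literature cannot be evidence for slower infusion. The Study design section says the trial is meant to generate an effect size for a later randomized trial or grant application. A reader planning that trial from the objective would be misinformed about what had been tested.

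**Working it through.** **Inputs.** Dose and duration per infusion come from the primary objective and hypothesis stem for this trial, and from the introduction and A. Significance for earlier work. Rate = dose (mg/kg) / duration (min).

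| Regimen | Dose / duration | Rate (mg/kg/min) | This trial's rate relative to it |
|---|---|---|---|
| This trial | 0.5 / 40 | 0.0125 | – |
| Earlier TRD report (introduction) | 0.5 / 40 | 0.0125 | 1.0 |
| 24-patient series | 0.5 / 40 | 0.0125 | 1.0 |
| 15-patient series | 0.5 / 40 | 0.0125 | 1.0 |
| 10-patient medication-free series | 0.5 / 40 | 0.0125 | 1.0 |
| 10-patient slow-infusion series | 0.3 / 100 | 0.0030 | 4.17 |

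The factor of 4.17 splits into duration, 100/40 = 2.5, and dose, 0.5/0.3 = 1.67. Giving 0.5 mg/kg at the slow-infusion rate would take 0.5/0.003 = 167 minutes. Among the earlier regimens for which the plan states both dose and duration, this trial is slower than none.

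**Dose.** Section 2.0 also says that the chosen dose is the highest in the literature and was selected for benefits already reported. That does not fit with calling it new.

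**What does differ.** Hypothesis 1 defines the conventional comparator as three infusions a week over 12 days, which is the 24-patient scheme. This trial gives 2 × 4 + 1 × 4 = 12 infusions over 8 weeks, a total of 12 × 0.5 = 6.0 mg/kg. The conventional scheme gives up to six, or 6 × 0.5 = 3.0 mg/kg. Eight of the 12 infusions here are in the twice-weekly phase, so *weekly* in the hypothesis stem is also wrong; the bold text just above it gives the schedule correctly.

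**Can a difference be credited to schedule instead?** Not to schedule alone. There is no concurrent control, and the documents record other differences:

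- Medication: the 24 patients "underwent a washout of antidepressant medication" and one 10-patient series was medication-free. Here, treatment-as-usual continues (C. Approach).
- Diagnosis: the reference title of the 24-patient series restricts it to major depression. This trial takes MDD and bipolar disorder.
- Response-based selection: this trial removes patients with less than a 30% MADRS reduction by the 4th treatment (Non responders). The medication-free series enrolled earlier single-dose responders and continued only those with a 50% reduction on day 2.

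**Monitoring and cost.** An anesthesiologist attends every infusion, and the Data analysis section names no cost outcome and no record of anesthetic intervention. The design cannot show that monitoring is dispensable.

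**The case against.** The strongest reply is that this is wording. The delivered treatment is unambiguous, since the plan gives 40 minutes consistently. The primary outcome, MADRS remission, does not depend on the word *slower*, and no analysis in the Data analysis section estimates an effect of rate. Hypothesis 1 defines its comparator by frequency; hypotheses 2 and 4 to 6 refer only to conventional schemes. The study is declared preliminary, and in a single-arm open-label design even a longer infusion would not allow causal attribution. All of this stands, and it limits the consequence. It does not make the objective correct: infusion time is what the objective and the innovation statement claim, and correcting them changes what the trial can be said to have tested.

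A reader might infer more than the documents support, in three ways.

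- That all the conventional series differ from this trial in medication, diagnosis and response-based stopping. Medication status is not given for the 15-patient series. A population limited to major depression is supported only by the title of the 24-patient series. The medication-free 10-patient series had its own, stricter response rule.
- That twice as many infusions must raise the share of patients with a hemodynamic event. That concerns the number of infusions, not their rate. Its size would rest on stopping and within-patient correlation figures that the plan does not give, and any such effect would work against hypothesis 6.
- That the remission result is compromised. It is not.

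**Conclusion.** The claims of a slower infusion and of a new dose and infusion time are wrong as written. Dose, duration and rate equal those of the conventional regimen (ratio 1.0), and the rate is about 4.2 times that of the only slower regimen described. No efficacy, tolerability or hemodynamic finding can be credited to slower infusion, and no difference from the historical series can be credited to schedule alone. The MADRS remission estimate is unchanged, and no sample-size or error-rate figure is involved. The conclusion rests only on doses and durations printed in the plan; it says nothing about earlier regimens whose duration the plan does not give. The *weekly* wording and the monitoring expectation are secondary.

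**What to change.** 1. Delete *slower* from the primary objective and the claim of a new dose and infusion time from B. Innovation.
2. Restate the objective around the schedule: 0.5 mg/kg over 40 minutes, twice weekly for 4 weeks and then weekly for 4 weeks, up to 12 infusions. Correct *weekly* in the hypothesis stem to match.
3. Frame hypotheses 1, 2 and 4 to 6 as descriptive comparisons with historical series, and state that no difference will be attributed to infusion rate or to schedule alone.
4. Next to them, list only the documented differences, series by series: schedule; washout (24 patients) or medication-free status (10 patients) against treatment-as-usual; major depression only, per its reference title (24 patients), against MDD plus bipolar disorder; and the 30% rule here against earlier responders with a 50% day-2 rule (10 patients).
5. Delete the expectation about anesthetic monitoring and cost.

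The cost is rewording, with no change to treatment, assessments or sample size; the downside is more modest claims. If the sponsor does want to study slow infusion, the infusion must be longer than 40 minutes. That would change the treatment, and without a control arm it would still not isolate the effect of rate.

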Routine blood tests will be performed in fasted state before the first ketamine infusion, prior to infusions at week 4 and at week 8. These tests aim to test the participants' overall health state. Blood samples will also be used for genetic testing and to measure levels of inflammatory markers. Samples will be stored at [REDACTED]. As stated in the consent form, participants will not receive any medical results or genetic counseling by providing a sample. All participants will undergo urine drug tests before each ketamine infusion.

Clinical questionnaires (e.g. MADRS) will be administered at baseline, at weeks 4, 8, and Week 12. The PANSS and Q-LES-Q scale will be administered after each ketamine infusion is completed. During the course of infusions, patients will receive treatment-as-usual from their primary psychiatrists as would be the case in a traditional therapeutic setting. There will be no changes in medication regimen throughout the 8 week treatment period as well as the 4 week observational follow-up period. Participants will be provided with a contact card directing them to the nearest ER/physician in case of emergency. Participants will be contacted weekly during the 4 week observational period to review the patient's health status and administer clinical scales. Upon conclusion of the intervention patients will be offered the opportunity to come back for maintenance sessions. The frequency of these sessions will depend on the patient's wishes and the physician's clinical judgment. The maximum session frequency will be once every month for a maximum of 12 months.

Assessment

The protocol consists of two components: clinical and cognitive assessments.

Clinical assessment

This evaluation will obtain family history and demographic data. Copies of any recent medical evaluations (past medical history, physical exam, etc.) will be requested from treating clinicians and health care providers. We will perform a urine drug screening (UDS) to rule out recent undisclosed use illicit substances. Demographic information is obtained through a standardized form and covers: age, race, gender, education (information both on siblings and their parents), religion, and socioeconomic status. Participants will fill out mood questionnaires rating the severity of the clinical symptoms.

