-MINI Interview: This is the standard psychiatric research evaluation for ascertainment of psychiatric diagnosis in the context of research studies (Sheeha et al., 2016)). It is a comprehensive structured interview for determining axis I diagnosis according to the DSM-V.

-Clinical Global Impression Scale (CGI): This is a clinical instrument to assess global changes in patients' status in clinical studies. We will use the CGI-BD, for use with BD patients (Guy et al., 1976).

-Montgomery-Åsberg Depression Rating Scale (MADRS): this scale rates depressive symptoms, and its psychometric properties are well-established (Montgomery et al. 1979).

-Young Mania Rating Scale (YMRS): This is a well-established clinical severity rating scale for manic symptoms that has adequate inter-rater reliability and internal consistency (Young et al., 1978).

- Quality of Life Enjoyment and Satisfaction Questionnaire (Q-LES-Q): this scale is patient-reported and measures the degree of enjoyment and satisfaction experienced by subjects in various areas of daily functioning (Endicott et al., 1993).

-

- The Positive and Negative Syndrome Scale (PANSS) includes 30- items and was conceived as an operationalized, drug-sensitive instrument that provides balanced representation of positive and negative symptoms. It is composed of four scales measuring positive and negative syndromes, their differential, and general severity of illness. The Positive and Negative Syndrome Scale (PANSS) for Schizophrenia. Kay, Stanley R.; Fiszbein, Abraham; Opfer, Lewis
A. Schizophrenia Bulletin, Vol 13(2), 1987, 261-276. This scale will be administered following each ketamine infusion to assess acute changes in mood.

Self-report questionnaires to assess mood and anxiety:

1. Adult (Brief Dissociative Experiences Scale [DES-B]—Modified): Frequency: After every injection, to monitor the dissociative side effects, Scale features: simple, easy to use, new DSM-5 self-rated scale
2. Severity Measure for Generalized Anxiety Disorder—Adult : Every 4 weeks, to measure the severity of anxiety. Scale features: simple, easy to use, new DSM-5 self-rated scale
3. Snaith–Hamilton Pleasure Scale: every 4 weeks, to measure the level of anhedonia, Scale features: easy to use, used before in ketamine studies, self-rated scale

Cognitive assessment

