The BAC-A is based on the Brief Assessment of Cognition in Schizophrenia (BAC-S). The BAC-S has been validated both linguistically and psychometrically in a number of psychiatric populations, including patients with schizophrenia and BD (Cuesta et al., 2011; Hill et al., 2013; Kuswanto, Sum, & Sim, 2013; Salgado et al., 2007; Segarra et al., 2011). It has been shown to be as valid and sensitive as a traditional neuropsychological assessment and takes approximately 35 minutes to administer (Keefe et al., 2004; Velligan et al., 2004). Six of the 8 subtests of the BAC-A match those found in the BAC-S. These tests are the Token Motor Task, Symbol Coding, List Learning, Digit Sequencing Task, Category Instances (Animals) and

Controlled Oral Word Association Test (F and S-words), Tower of London (Keefe et al., 2004). In addition to these 6 subtests the BAC-A comprises the Emotion Inhibition Test (a modified version of the Emotional Stroop task (LaMonica, Keefe, Harvey, Gold, & Goldberg, 2010; Williams, Mathews, & MacLeod, 1996)) and the affective auditory verbal learning test (Affective interference test). The latter task is similar to the Affective Auditory Verbal Learning Test (AAVLT) (Snyder & Harrison, 1997). Assessments will be conducted prior to the treatment period, 4, and 8 weeks into the treatment. To avoid potential learning bias we will use parallel versions of the word lists for the Emotion Inhibition Test, Tower of London, and the Verbal Memory Tests to assess cognitive changes over the course of the ketamine treatment.

Study design

We will follow an AB design and clinical/cognitive assessments will be taken at baseline, week 4, week 8, and week 12. Given the preliminary nature of this treatment study this open label trial aims to generate an effect size for a subsequent RCT and/or future grant application. No *a priori* estimates of the power/effect size were therefore calculated.

Timeline	After Each Infusion	Baseline	Week 4	Week 8	Weekly Follow-up Phone Calls	Week 12
SCID-I		X				
Clinical scales (MADRS, CGI, YMRS)		X	X	X	X	X
PANAS, Q-LES-Q, self-report	X					
BAC-A		X	X	X		X
Blood tests/Sample		X	X	X		X
Urine drug test	X	X				

Study sample

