- 12) Pregnancy or Breast feeding. All female in reproductive age will undergo pregnancy tests. Female participants will be required to provide evidence of use of contraceptives during the course of the study.
- 13) Unable to understand the design and requirements of the study
- 14) Unable to sign the informed consent for any reason
- 15) An assigned responsible adult has provided assent to assist in patient's study participation. The responsible adult agrees to be present at each study appointment as well as provide transportation to study appointments for the patient.

Non responders

If a patient does not respond to the study treatment by their 4th treatment they will be removed from the study due to non-response. A successful response to study treatment will be at least a 30% reduction in MADRS scores from screening until the 4th treatment. Again if a patient does not respond by the 4th treatment, they will be excluded from the study.

Unanticipated Hospitalizations

If a patient needs to be hospitalized for worsening of symptoms or for their own personal safety, they will be removed from their study participation and their study treatment will end at that time.

Feasibility

Subject recruitment: Our center has access to a large patient pool (drawing from a metropolitan area of about 5.5 million people) and well-established ability to recruit patients with mood disorders. [name] is the department chair for Psychiatry and Behavioral Sciences and Director of the University of Texas, Center of Excellence on Mood Disorders. He successfully completed a large number of studies over the past 20 years with excellent recruitment of MDD and BD subjects at this site. We will also recruit participants through doctor referrals. Participants will be exclusively outpatients.

Funding of the study: given the preliminary nature of this study we plan to use departmental funding for the current study and then possibly apply for a larger grant later on once we have collected preliminary data and calculated optimal power/effect sizes for ketamine treatment in individuals with TRD.

Data analysis

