The subjects will include males and females, ages 18-65 years old, from various race/ethnic backgrounds, as reflected in the local community in the greater Houston area.

Inclusion of Minorities

Our study will include minority groups in proportions that will be representative of the ethnic/racial composition of the local community in Houston, Texas. Our projected numbers for minority enrollment are detailed in the enrollment table attached.

Inclusion of Children

Children will not be included in the study. The inclusion of children at this early stage would increase substantially the number of subjects needed for the overall project. At this time, we will focus on an adult population (ages 18-65 years old), which will also allow us to limit some of the potential confounding factors to our brain imaging and neurocognitive findings. Depending on our results these investigations will be extended to children and individuals over 65 years old in future studies.

Prisoners and pregnant women

We are aware of the special protections afforded to prisoners per federal regulations. We will not actively recruit people who are incarcerated to participate in this study. We do, however, acknowledge the possibility of research participants in our target population being incarcerated during the study. If an active participant is incarcerated for an extended period of time, disenrollment from the study will be necessary. No research interaction or intervention will take place until an incarcerated participant is released from jail. Finally, neither pregnant woman nor neonates will be enrolled in this study.

Potential Risks

Loss of confidentiality is a highly unlikely but potential risk associated with this study. Some participants may find questions annoying or intrusive and neuropsychological testing might induce some fatigue and sensation of boredom. The venipuncture (insertion of small IV due to need for IV infusion of ketamine) might produce some mild pain, bruising, bleeding, infection, and in some cases even induce fainting. Side effects associated with ketamine injection are rare and, if any, of transient duration. The most commonly reported side effects during the 4-hour period after each infusion include feeling strange or unreal (58.3%), abnormal sensations

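### Hypothesis 2 measures psychiatric side effects on mood scales, chiefly the efficacy scale, and is insensitive to the acute post-infusion effects the protocol cites; the DES-B collected after every injection is tied to no hypothesis

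*Combined protocol and SAP*

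**What the plan says.** All references are to the combined protocol and SAP.

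- **The hypothesis.** In the list under the primary objective, hypothesis 2 is that patients will "Report less psychiatric side effects measured by changes in test scores on the Montgomery-Åsberg Depression Rating Scale (MADRS", with QIDS and YMRS named after it, relative to earlier reports on conventional serial infusion schemes.
- **The other role of MADRS.** Section 2.0, A. Significance (last paragraph), makes MADRS-based remission the primary outcome. The instrument list under Clinical assessment describes MADRS as rating depressive symptoms.
- **When the scales are rated.** C. Approach: "Clinical questionnaires (e.g. MADRS) will be administered at baseline, at weeks 4, 8, and Week 12". In the schedule table under Study design, the row beginning "Clinical scales (MADRS, CGI, YMRS" is marked at baseline, weeks 4, 8 and 12 and the phone calls, but not in the after-each-infusion column. The calls come after treatment: "Participants will be contacted weekly during the 4 week observational period". The Non responders section implies one further MADRS: "A successful response to study treatment will be at least a 30% reduction in MADRS scores from screening until the 4th treatment". QIDS is in neither the instrument list nor the schedule.
- **The side effects expected.** Potential Risks: "The most commonly reported side effects during the 4-hour period after each infusion include feeling strange or unreal (58.3%), abnormal sensations", followed by further rates. A. Significance describes psychotic or dissociative symptoms in a 10-patient repeated-dose series as minimal and transient.
- **What is collected after each infusion.** The DES-B is given "After every injection, to monitor the dissociative side effects". The text also places the PANSS after each infusion, where the schedule table has PANAS. Hypothesis 3 uses PANSS to show an almost immediate effect. No hypothesis uses the DES-B.

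**The concern.** A side-effect measure should move when side effects occur and stay still when they do not. MADRS is designed to move with depression. If ketamine works, MADRS falls, and hypothesis 2 reads that fall as better psychiatric tolerability as well as benefit. Patients could dissociate after most infusions and the hypothesis could still be supported, because its scales are not scheduled to capture acute effects.

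Hypothesis 2 is the only hypothesis that defines psychiatric side effects. The stated purpose of the trial includes showing that this approach needs less monitoring, and its results are meant to inform a later RCT. A tolerability statement resting on these scales would carry forward without saying anything about the effects the protocol itself lists as most common.

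**Working it through.** **1. The cited rates.** Potential Risks attributes the rates to the repeated-infusion study that A. Significance gives as 24 patients. Taking 24 as the denominator (an assumption):

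- 14/24 = 58.3%
- 13/24 = 54.2%
- 12/24 = 50.0%
- 11/24 = 45.8%

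All four reproduce, so they look like per-patient proportions. Only the first, feeling strange or unreal, is clearly psychiatric; blurred vision and drowsiness are not. Applied to the planned sample: 30 × 0.583 = 17.5 patients.

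**2. Overlap between ratings and infusions.** Number of infusions: 2 × 4 weeks + 1 × 4 weeks = 12, matching the Reimbursement section.

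| Scale | Ratings during treatment | Infusions that could coincide with a rating |
|---|---|---|
| YMRS | weeks 4 and 8 | at most 2 of 12 |
| MADRS | weeks 4 and 8, plus one implied by the 4th treatment | at most 3 of 12 |
| QIDS | none scheduled | 0 of 12 |
| DES-B | after every injection | 12 of 12 |

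These are upper limits. The rating time relative to that week's infusion is not stated; if ratings precede the infusion, the first two rows fall to 0 of 12 within the 4-hour window.

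**3. Direction of MADRS.** Two features push MADRS towards apparent good tolerability.

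- An antidepressant response lowers it.
- Patients with less than a 30% reduction by the 4th treatment leave the study, as do those hospitalised for worsening. Week 4 and week 8 values then come from patients already selected for improvement.

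The documents give no figures from which to size the second effect, so only its direction is claimed.

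**4. Can the hypothesis fail?** Yes. It is comparative. The MADRS figure quoted for a conventional scheme is an 85% reduction after six infusions, in 10 patients preselected for response to a single dose. A smaller fall here would count against hypothesis 2, and so would a clear rise in YMRS. Neither route depends on how many patients dissociate.

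**5. Is there a comparator for an acute measure?** The documents give no earlier DES-B value. The nearest figure, 14/24, differs in three ways:

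- it covers 4 hours, against a 2-hour observed rest here;
- it comes from up to six infusions, against 12 here, so a proportion with any event is not on the same footing;
- it is imprecise, with an exact 95% interval of 36.6% to 77.9%.

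As an illustration, assume the same item was recorded in both studies, all 30 patients are evaluable, and a two-sided 5% Fisher test is used. Showing a lower rate than 14/24 would then need 8 or fewer affected of 30. The chance of that is 0.87, 0.43 and 0.09 if the true rate is 20%, 30% and 40%. Data analysis describes paired tests within the study and names no side-effect outcome, comparator value or test against earlier reports.

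**The case against.** The strongest reply has four parts.

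- **The acute effects are recorded.** DES-B and PANSS (or PANAS) follow each infusion, staff question patients throughout, and psychiatric screening is planned during each infusion. This stands. A reader might infer that dissociation would go unseen, and the documents do not support that. The gap is that these data are not linked to the hypothesis about side effects.
- **YMRS has a precedent.** The cited slow-infusion study used YMRS to assess psychiatric side effects, and manic symptoms matter in a sample that includes bipolar disorder. This stands, and is why YMRS should be kept. That study paired it with a general psychiatric scale, the BPRS; hypothesis 2 pairs it with two depression scales.
- **Ratings may fall near an infusion.** Weeks 4 and 8 are infusion weeks, so a rating there is at most days from an infusion and could lie inside a 4-hour window. This also stands. It limits the criticism to infrequent ratings at unstated times; the documents do not show that the scales are always read weeks after an infusion.
- **This is a non-primary hypothesis in a preliminary open-label study.** True: the primary outcome, remission, is untouched. It is also too much to call hypothesis 2 the main tolerability claim, since better tolerability appears in hypothesis 1, with hemodynamics in 6 and cognition in 7. But hypothesis 1 names no measure, so the psychiatric part rests on hypothesis 2.

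**Conclusion.** The point holds in a limited form. Hypothesis 2 mixes efficacy with tolerability through MADRS, names a scale (QIDS) that is not scheduled, and is insensitive to the acute effects the protocol cites. It could be supported whatever their rate. At the cited 58.3%, about 17 or 18 of 30 patients would feel strange or unreal, while scheduled ratings could coincide with at most 2 of 12 infusions for YMRS and 3 of 12 for MADRS.

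A reader might go further and infer that the hypothesis cannot fail. The documents do not support that: a MADRS fall short of the cited 85%, or a rise in YMRS, would count against it. Nor do they predict any particular YMRS value in this trial.

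The conclusion assumes that 24 is the denominator of the cited rates and that the schedule is followed as written. The overlap counts are maxima because rating times relative to infusion are not given.

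**What to change.** 1. Remove MADRS and QIDS from hypothesis 2. Keep MADRS for efficacy.
2. Make the DES-B the acute psychiatric side-effect outcome. Report it per infusion and as the proportion of patients with any event, with the definition of an event and the number of infusions received.
3. Reconcile PANSS in the text with PANAS in the schedule table. If the scale is PANSS, report it after each infusion as supporting evidence.
4. Keep YMRS as a separate outcome for manic symptoms.
5. State the time of every rating relative to the infusion.
6. Report the DES-B result descriptively. With no earlier DES-B value in the documents, and a 2-hour rest set against a 4-hour benchmark window, do not claim from it that side effects were fewer than previously reported.

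The cost is rewording and an addition to the analysis section; the DES-B is already collected, so no new assessment is needed. The small downside is that the tolerability result may look less favourable than it would on MADRS and YMRS.
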